[name] ^{1, 5}	PhD student	Wrote the study protocol, Co-Investigator		20.07.2020
[name] ^{1, 3}	PhD student	Wrote the study protocol, Co-Investigator		07.07.2020
[name] ¹	RM, [name], PhD	Wrote the study protocol, Co-Investigator		15.07.20
[name] ^{2, 3}	[name], Chief Physician	Wrote the study protocol, Co-Investigator		9/7-2020

Affiliation

- ¹ University of Copenhagen, Department of Biomedical Sciences, Copenhagen, Denmark
- ² University of Copenhagen, Department of Clinical Medicine, Copenhagen, Denmark
- ³ Nordsjællands Hospital, Department of Gynecology and Obstetrics, Hillerød, Denmark
- ⁴ Nordsjællands Hospital, Department of Clinical Research, Hillerød, Denmark
- ⁵ University of Copenhagen, Department of Public Health, Biostatistics, Copenhagen, Denmark

Section 2: Introduction

Background and rationale

Pregnancy can be a great chance to implement good habits, such as physical activity, as pregnant women are in regular contact with health professionals and may be motivated to adopt healthy

behaviors as evidenced by reduced alcohol consumption and smoking cessation [1–3]. Structured supervised exercise training and motivational counseling constitute two very different approaches to implement and maintain a physically active lifestyle. Both approaches have been applied separately in pregnant women [4–23], but the relative efficacy of structured supervised exercise training and motivational counseling has not previously been compared in pregnant women. In the FitMum randomized controlled trial (RCT), we will test the efficacy of two exercise approaches versus a control group on physical activity level, which will be measured objectively by a consumer activity tracker in all three trial groups. The two exercise programs are structured supervised exercise training (EXE) and motivational counseling (MOT), respectively. The control group (CON) will receive usual care.

Objectives and hypotheses

Primary objective

- The primary objective is to investigate the effects of EXE and MOT on moderate to vigorous physical activity (MVPA) in pregnant women.

The hypotheses are:

1. EXE is more effective than MOT to increase MVPA in pregnant women
2. MOT is more effective than usual care (CON) to increase MVPA in pregnant women.

Secondary objective

- The secondary objective is to investigate the effects of EXE and MOT on gestational weight gain (GWG).

The hypotheses are:

1. Pregnant women in the EXE group gain less weight than those in the MOT group
2. Pregnant women in the MOT group gain less weight than those in the CON group.

Exploratory outcomes

- Complementary data on levels of physical activity are determined using doubly labeled water, questionnaires, and additional data from the activity tracker.
- Clinical and metabolic health parameters in mother and offspring.

Section 3: Study Methods

Trial design

Single-site three-armed randomized controlled trial.

Brief description of the interventions

The targeted physical activity level for all participants in the EXE and MOT groups is at least 30 minutes per day at moderate intensity as recommended to healthy pregnant women [6].

Standard care control group (CON)

The CON group is offered standard care at the hospital.

Structured supervised exercise training (EXE)

The training is performed in groups and supervised by health professionals. It consists of three weekly one-hour exercise sessions at a moderate intensity, including two land exercise sessions and one water exercise session.

Motivational counseling supported by health technology (MOT)

This intervention comprises four individual and three group counseling sessions during the pregnancy as well as weekly SMS-reminders. The overall focus of both the individual and group counseling sessions is to create a climate that taps into what already motivates the participants to increase or maintain their physical activity level. The activity trackers are used as an intervention element to motivate the participants to increase their physical activity levels. The weekly SMS-reminders have supportive and motivating content and are used to encourage the participants to achieve a moderate physical activity level.

Changes of the intervention during the COVID-19 pandemic

During the COVID-19 pandemic, EXE is converted to exercise at home with online group sessions. MOT is also held online. As much data as possible will be collected during the pandemic, but some clinical data may not be possible to obtain.

Randomization

After a one-week baseline period where the physical activity level is measured by the activity trackers, the women are randomly assigned in a 1:2:2 ratio to CON, EXE or MOT. The randomization is performed via a numbered randomization list administered through the electronic database REDCap and the investigators are blinded to the randomization procedure.

Sample size

[figure not shown]
Primary outcome

The sample size has been calculated for physical activity level among pregnant women from randomization to GA week 28+6. We consider a scenario with a comparison of three groups (CON, EXE and MOT). It is assumed that the two interventions have a positive effect, and we stipulate that the average activity levels in the three groups are 60, 210 and 150 min/week, respectively. The stipulations are based on the participants in the intervention groups reaching the target of being physically active for at least 30 min/day (7 x 30 min/day = 210 min/week). Also, we would like to be able to detect a difference in the weekly activity level of 60 min/week. Therefore, an activity level of 150 min/week is stipulated in one of the intervention groups. Lastly, the activity level in CON is stipulated to be 60 min/week as structured exercise at moderate to vigorous intensity for more than one hour/week is an exclusion criterion. Based on a literature study [10], we estimate that the standard deviations in the three groups are the same and equal to 116 min/week. We assume that data are normally distributed. We require a power of 80%.

We consider the alternative hypothesis that the average activity levels in the three groups are significantly different from each other and the average activity levels in the two intervention groups are also significantly different from each other (a double hypothesis). We calculate the required sample size by simulation using a likelihood ratio test at a joint significance level of 5% for the two hypotheses

using a Bonferroni correction. We choose to randomize to the ratio 1:2:2 (CON:EXE:MOT) as this requires the lowest number of participants, and gives the participants (who we assume are motivated for being more physically active) the greatest chance of being randomized to an intervention group. In order to obtain the required power, 35 participants in the CON group and 70 participants in EXE and MOT groups are required, and hence 175 participants in total (Figure 1).

Figure 1: Overview of the sample size of participants needed in the control group to reach a strength of 80 %, considering scenario characterized by having the double number of people in each intervention group relative to the number in the control group (2:2:1 randomization).

The expected lost-to-follow-up rate needs to be considered and added to the sample size. Therefore, we will include 44 participants in CON and 88 participants in EXE and MOT, respectively, in total 220 women, based on an expected lost-to-follow-up rate of 20%, as seen in similar exercise studies in pregnant women [6,10,12,19]. This should leave 35 participants in CON (0.8×44) and 70 participants in each of the two intervention groups (0.8×88), which will give sufficient power for analysis of the primary outcome.

Secondary outcome

Based on a comparable intervention study with exercise training [21], the estimated GWG in the intervention and control groups had standard deviations of 4 kg. Thus, in the present study, 33 women in the CON and 66 in each of the intervention groups (EXE and MOT) are needed to detect a difference of 2.8 kg between the control and the intervention groups with a power of 0.80 and two-sided α -level of

0.05. The sample size calculation to this secondary outcome was performed during the intervention but before the intervention was completed.

Framework

The hypothesis testing framework is based on model comparisons using the Likelihood Ratio Test of equality between null and alternative models.

Statistical interim analyses

No interim analyses will be performed. The trial will not be stopped early as a result of data analyses.

Timing of final analysis

The final analysis of the primary outcome will be performed when the last participant has passed GA week 28+6. The final analysis of the secondary outcome will be performed when the last participant gives birth.

Timing of outcome assessments

The primary outcome is measured continuously (24/7) from randomization to GA week 28+6. The secondary outcome is measured at baseline (max. GA week 15+0), GA week 28+0-6, GA week 34+0-6 and at delivery.

Section 4: Statistical Principles

Confidence intervals and P values

The level of statistical significance is 5%. The primary analysis containing two hypotheses will be tested at a significance level of 2.5% each to control the family-wise type I error. Wald-based 95% confidence intervals will be given for all reported estimates.

Adherence, protocol deviations, and analysis populations

The primary analysis is an intention-to-treat analysis including all participants as randomized. Also, a dose-response model will be fitted for the EXE and MOT groups to describe the relationship between adherence to the intervention (proportion of attendances) and the attained activity level. This relationship will be compared to the average activity level in the CON group.

Section 5: Trial Population

Screening data

Screening data will not be reported.

Eligibility

Inclusion criteria

- Written informed consent obtained before any trial-related procedures are performed
- A pregnant woman aged 18 years or older
- GA of max. 15+0 weeks
- Ultrasonic confirmed intrauterine pregnancy
- BMI of 18.5-45 kg/m² and body weight below 150 kg calculated from pre-pregnancy weight or first measured weight in pregnancy

- Ability to wear a wrist-worn activity tracker 24/7

Exclusion criteria

- Severe chronic disease
- Structured exercise at moderate to vigorous intensity more than 1 hour per week during pregnancy
- Previous preterm delivery (before GA week 37)
- Obstetric or medical complications
- Multiple pregnancies
- Non-Danish speaking
- Alcohol or drug abuse

Recruitment

The flow chart of the trial will follow the CONSORT guidelines and will include the number of individuals who a) showed interest to participate in the study by filling out a pre-screening questionnaire, b) were assessed for eligibility at screening visit, c) were included in the trial, d) were randomized, e) did not receive allocated treatment, f) were lost to follow-up, g) discontinued the intervention, and h) were analyzed in the end.

Withdrawal/lost to follow-up

If a randomized participant withdraws or is discontinued from the intervention, we will offer to perform all or some of the planned visits. The number/frequency of participants lost to follow-up will be provided for each group and for each visit. If possible, the reasons for participants not completing the trial will be given. Summary of baseline levels for variables reported in the baseline table will be provided for completers and non-completers.

Baseline patient characteristics

Categorical variables will be summarized by frequencies and proportions, and symmetrically distributed continuous variables will be summarized by the mean and standard deviation (SD). Asymmetric variables will be presented as medians and interquartile ranges (IQR).

The table presents the baseline characteristics to be reported.

Number of participants	N=220
Age (years)	Mean ± (SD) or median (IQR)
Weight (kg)	Mean ± (SD) or median (IQR)
BMI at inclusion (kg/m ²)	Mean ± (SD) or median (IQR)
Gestational age at inclusion (weeks)	Mean ± (SD) or median (IQR)
Education level (1-3)	n/Total (%)

The number of babies (no.)	Mean ± (SD) or median (IQR)
Marital status (married or have partner/not)	n/Total (%)
Alcohol consumption before pregnancy (serving/week)	Mean ± (SD) or median (IQR)
Alcohol consumption during pregnancy (serving/week)	Mean ± (SD) or median (IQR)
Smoking status (current smoker)	n/Total (%)
Employed (yes/no)	n/Total (%)
Physical activity at work (active/sedentary)	n/Total (%)
Fertility treatment (no.)	n/Total (%)
Self-reported weekly physical activity level during pregnancy before inclusion (≤30 minutes or 30-60 minutes)	n/Total (%)
Minor health problems (no.)	n/Total (%)
Pelvic pain during pregnancy (yes/no)	n/Total (%)
Pelvic pain before pregnancy (yes/no)	n/Total (%)
Total cholesterol (mmol/L)	Mean ± (SD) or median (IQR)
HDL (mmol/L)	Mean ± (SD) or median (IQR)
LDL (mmol/L)	Mean ± (SD) or median (IQR)
HbA1c (mmol/mol)	Mean ± (SD) or median (IQR)
Triglycerides (mmol/L)	Mean ± (SD) or median (IQR)
Steps per day (average steps/day)	Mean ± (SD) or median (IQR)
Active calories (calories/day)	Mean ± (SD) or median (IQR)
Moderate to vigorous physical activity (minutes/week)	Mean ± (SD) or median (IQR)
Active time (minutes/day)	Mean ± (SD) or median (IQR)
Floors walked (no./week)	Mean ± (SD) or median (IQR)
Minimum heart rate (beats/min)	Mean ± (SD) or median (IQR)
Average heart rate (beats/min)	Mean ± (SD) or median (IQR)
Maximum heart rate (beats/min)	Mean ± (SD) or median (IQR)
Resting heart rate (beats/min)	Mean ± (SD) or median (IQR)
Metabolic equivalent of task (MET/day)	Mean ± (SD) or median (IQR)
Move IQ (%type of physical activity)	Mean ± (SD) or median (IQR)

Section 6: Analysis

Outcome definitions

Primary outcome

The primary outcome, MVPA, is measured continuously (24/7) by an activity tracker and will be presented in minutes per week from randomization to GA week 28+6.

Secondary outcome

The secondary outcome is GWG, i.e. weight gained from the onset of the pregnancy to giving birth. GWG is determined as the difference between body weight on the day of birth and preconception body weight.

All other outcomes will not be presented with hypothesis testing, and they will be represented as exploratory outcomes.

Analysis methods

The treatment effects for the primary and secondary outcomes will be presented as mean differences between the treatment groups adjusted for physical activity at baseline. These values will be estimated from a multiple linear regression model. Analysis of the primary outcome based on multiple imputed datasets will be performed as a sensitivity analysis. The imputations will be performed using the R package “mice” [24]. 25 imputed data sets will be generated using the seed 24658. The imputations will be constructed on the following baseline covariates (body weight, age, group allocation, physical activity at baseline, socio-economic status). In addition, a sensitivity analysis will be performed to investigate whether the COVID-19 pandemic had an impact in the three study groups.

Missing data

The primary outcome will be measured by the activity tracker continuously (24/7) during the intervention. Possible missing data from the tracker due to not wearing the device or other reasons (e.g. skin rash) will be handled according to the predefined inclusion of the data in the analysis. For the primary outcome, a week will be included in the analysis if the week has four or more days with complete data. A day that has six hours or more of non-wear time will be excluded and considered a missing day.

Additional analyses

Analyses describing associations between the level of physical activity, as measured by the activity tracker, and the secondary and exploratory outcomes in all three groups will be performed.

Harms

Information about adverse events (AEs) and serious adverse events (SAEs) will be registered and reported. The AEs/SAEs will be reported as frequency and percentage in the trial groups.

Statistical software

The statistical analysis will be performed using the latest version of R [24].

References

- [2] World Health Organisation (WHO). *Good Maternal Nutrition. The best start in life.* 2016.

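### Normal MVPA with an SD of 116 min/week is impossible in CON at a mean of 60, and the primary analysis has no safeguard if the arm variances differ

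*SAP*

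**What the plan says.** In Section 3, under the primary-outcome sample size, the SAP stipulates that the "average activity levels in the three groups are 60, 210 and 150 min/week, respectively" for CON, EXE and MOT. On spread it says "we estimate that the standard deviations in the three groups are the same and equal to 116 min/week", citing an earlier trial, and on shape "We assume that data are normally distributed". The target is 80% power, reached by simulation "using a likelihood ratio test at a joint significance level of 5% for the two hypotheses", with 1:2:2 allocation and 35/70/70 evaluable women.

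Section 6, Analysis methods, defines the treatment effects as mean differences adjusted for baseline activity: "These values will be estimated from a multiple linear regression model". Section 3, Framework, bases testing on likelihood ratio comparisons of null and alternative models. Section 4 allots 2.5% to each of the two primary hypotheses and adds "Wald-based 95% confidence intervals will be given for all reported estimates".

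No robust standard error, arm-specific variance, bootstrap or residual check is named for the primary outcome. Its sensitivity analyses concern multiple imputation and COVID-19. The baseline table allows for asymmetric variables; the outcome analysis makes no similar allowance.

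**The concern.** Weekly minutes of activity cannot be negative. A normal distribution whose mean is about half its SD puts much of its mass below zero, so the planning description of CON cannot be right as a whole. At least one part must give way, and the SAP does not say which or what the analysis would then do.

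The equal SD is also open to doubt on the plan's own reasoning. The CON mean is set at 60 because women doing more than one hour of structured exercise per week are excluded, yet this low-mean arm gets the same spread as arms averaging 150 and 210.

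Ordinary linear regression estimates one residual variance from all three arms and uses it for every contrast. If CON differs in spread, each contrast gets the wrong standard error: EXE–MOT because it borrows CON's variance, MOT–CON because the arms also differ in size. At stake are the 2.5% level of each primary test and the coverage of the reported intervals.

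**Working it through.** **Inputs from the SAP.** Means 60/210/150 (CON/EXE/MOT), SD 116, evaluable n 35/70/70, two-sided 2.5% per test (critical value z = 2.241).

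**The plan's own figure.** I read the sample-size target as requiring both the overall three-group test and the EXE–MOT test, each at 2.5%. Simulating this with normal data and a pooled-variance likelihood ratio test gives 79.7% power at 35/70/70. As a check, EXE–MOT alone has SE = 116 × √(2/70) = 19.61, so power = Φ(60/19.61 − 2.241) = 79.4%. The sample size follows from its inputs.

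**Share below zero, Φ(−mean/SD).**
- CON: Φ(−60/116) = 30.2%
- MOT: Φ(−150/116) = 9.8%
- EXE: Φ(−210/116) = 3.5%

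**Effect of one pooled variance.** The arm SDs below are assumptions, without baseline adjustment.
- Pooled variance: s² = Σ(nᵢ − 1)SDᵢ² / 172
- Model SE: √[s²(1/nᵢ + 1/nⱼ)]
- True SE: √(SDᵢ²/nᵢ + SDⱼ²/nⱼ)
- Type I error: 2·P(Z > 2.241 × model SE / true SE)

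For 60/116/116: s² = (34 × 3600 + 138 × 13456)/172 = 11507.7, so s = 107.3.
- EXE–MOT: model SE 18.1, true SE 19.6, ratio 0.925; type I error 3.8%.
- MOT–CON: model SE 22.2, true SE 17.2, ratio 1.29; type I error 0.4%.

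| SD CON/EXE/MOT | s | EXE–MOT SE, model / true | Type I error | MOT–CON SE, model / true | Type I error | Sum |
|---|---|---|---|---|---|---|
| 116/116/116 | 116.0 | 19.6 / 19.6 | 2.5% | 24.0 / 24.0 | 2.5% | 5.0% |
| 100/116/116 | 113.0 | 19.1 / 19.6 | 2.9% | 23.4 / 21.9 | 1.6% | 4.5% |
| 80/116/116 | 109.8 | 18.6 / 19.6 | 3.4% | 22.7 / 19.4 | 0.9% | 4.2% |
| 60/116/116 | 107.3 | 18.1 / 19.6 | 3.8% | 22.2 / 17.2 | 0.4% | 4.2% |
| 116/60/60 | 74.5 | 12.6 / 10.1 | 0.5% | 15.4 / 20.9 | 9.8% | 10.3% |

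The sum (from unrounded values) is an upper bound on family-wise error when both nulls hold. Simulation (40,000 normal trials) gave about 4.1% for 60/116/116 and about 10% for 116/60/60.

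**Coverage of the 95% intervals.** For 60/116/116, EXE–MOT covers about 93% and MOT–CON about 99%. For 116/60/60, MOT–CON covers about 85%.

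**Skewness alone.** With non-negative gamma data and SD 116 in every arm, the pooled EXE–MOT test has a type I error of about 2.4% and power of 79.0%. Non-normality by itself does little at these arm sizes.

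**HC3.** In normal simulations, both tests return to about 2.4–2.5% with SDs of 60/116/116, and to 2.5–2.6% with 116/60/60.

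**The case against.** The case on the other side is substantial.

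- **Equal variance is not ruled out.** A reader might infer that the planning figures exclude equal SDs. They exclude only normality together with an SD of 116 at a mean of 60. A skewed outcome with SD 116 in every arm is possible, and the pooled tests are then nearly correct. This stands: all the harm comes from SDs the SAP does not state, and its direction reverses if CON is the more variable arm.
- **Family-wise control.** A reader might infer that the 5% level fails whenever CON is less variable. It does not: the inflated EXE–MOT error is offset by a deflated MOT–CON error, and the two sum to about 4%. Only a larger CON SD takes the family-wise error above 5%.
- **Power.** A serious loss for MOT–CON might be feared. The stipulated difference there is 150 − 60 = 90; the 60 in "we would like to be able to detect a difference in the weekly activity level of 60 min/week" separates EXE from MOT. At 90, with SDs 60/116/116, power is Φ((90 − 2.241 × 22.2)/17.2) = 99.0%, against 99.9% with the true SE. The cost is interval width.
- **Wording and adjustment.** Normality is stated as a sample-size input, and the SAP never mentions a pooled variance. That follows from ordinary linear regression with no alternative named. Baseline adjustment would lower the residual SDs, so the magnitudes are indicative, but it would not in itself make them equal.
- **GWG.** Extending the point to the secondary outcome has no support: the SAP gives an SD of 4 kg for both intervention and control groups.

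What the objection does not remove is the impossible combination in CON and the lack of any protection in the primary analysis.

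**Conclusion.** The point holds in conditional form. Mean 60, SD 116 and normality are jointly impossible for minutes of activity in CON, since 30% of women would fall below zero. The primary analysis then relies on one residual variance across unequal arms. If the SDs are equal, little is lost. If CON is less variable (SD 60 to 80 against 116), EXE–MOT is tested at 3.4–3.8% instead of 2.5%, and the MOT–CON standard error is 17–29% too large, with family-wise error still near 4%. If CON is more variable (116 against 60), MOT–CON is tested at about 9–10% and the family-wise level is broken. These sizes rest on assumed SDs, 35/70/70 evaluable women and no baseline adjustment. A reader might also infer that the sample size is wrong; it reproduces from its inputs and is not challenged. This is a worthwhile, inexpensive safeguard, not a fatal flaw.

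**What to change.** For the primary outcome only, keep the baseline-adjusted linear model, the untransformed outcome and the mean differences, and add one sentence to Section 6, Analysis methods. It should state either that tests and intervals use heteroscedasticity-consistent (HC3) standard errors, or that the null and alternative models are fitted with arm-specific residual variances. The second option keeps the likelihood ratio framework of Section 3; with HC3 the tests become Wald tests, so the Framework paragraph needs a matching edit. Fixing this in advance also removes a later data-driven choice of standard error.

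The cost is a line or so of R code, a slightly wider EXE–MOT interval if CON is less variable, and a trivial loss of precision if the SDs are equal. HC3 is also mildly liberal for MOT–CON if CON is strongly skewed with an SD of 116: about 3.2–3.5% for a nominal 2.5% (2.9% in an unadjusted gamma simulation with mean 60 in all arms).

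### The objectives and the sample size name different pairs of primary hypotheses, and the stated 80% power belongs only to the sample-size pair

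*SAP*

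**What the plan says.** The two primary tests are described in several places of the SAP, and not in the same way.

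- **Section 2, Primary objective** numbers two hypotheses. The first is that EXE raises MVPA more than MOT. The second is that "MOT is more effective than usual care (CON) to increase MVPA in pregnant women".
- **Section 2, Background and rationale** promises more broadly that "we will test the efficacy of two exercise approaches versus a control group on physical activity level".
- **Section 3, Sample size, Primary outcome** defines the alternative to be powered in two parts. The first part concerns all three arms: "We consider the alternative hypothesis that the average activity levels in the three groups are significantly different from each other". The second part is a contrast of EXE with MOT, and CON does not enter it. Power of 80% is required, using likelihood ratio tests and a Bonferroni split of a joint 5%. The result is 35/70/70 evaluable women (CON/EXE/MOT), raised to 44/88/88 for 20% loss, "which will give sufficient power for analysis of the primary outcome".
- **Section 3, Framework**: "The hypothesis testing framework is based on model comparisons using the Likelihood Ratio Test of equality between null and alternative models".
- **Section 4, Confidence intervals and P values**: "The primary analysis containing two hypotheses will be tested at a significance level of 2.5% each to control the family-wise type I error". The two hypotheses are not named here.
- **Section 6, Analysis methods** reports "mean differences between the treatment groups adjusted for physical activity at baseline" and names no contrasts.

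**The concern.** EXE vs MOT belongs to both pairs. The second test does not: it is MOT vs CON in the objectives and a three-group comparison in the sample size. The rule in Section 4 and the likelihood ratio framework fit either.

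The two pairs answer different questions. Suppose MOT did nothing (mean 60, equal to CON) and EXE reached 210. Both sample-size tests would then reject in essentially every trial, although the second listed hypothesis would be false. Success on the powered pair therefore says nothing about MOT against usual care.

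Two things are at stake. The p-value that decides the second primary claim is left open, so it could be settled after the results are seen. And if the listed pair is the tested one, the stated power was computed for something else. Under either pair EXE vs CON carries no alpha, although the background section says both programmes will be tested against control.

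**Working it through.** **Inputs (Section 3, Sample size; Section 4).** Means CON/EXE/MOT 60/210/150 min/week, so EXE−MOT = 60 and MOT−CON = 90. Common SD 116. Evaluable n 35/70/70. Each test at two-sided 2.5%, critical z = 2.241. No credit for baseline adjustment at this stage.

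**Single tests, normal approximation.**

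- EXE vs MOT: SE = 116 × √(1/70 + 1/70) = 19.61; 60/19.61 = 3.060; power = Φ(3.060 − 2.241) = 79.4%.
- MOT vs CON: SE = 116 × √(1/70 + 1/35) = 24.01; 90/24.01 = 3.748; power = Φ(3.748 − 2.241) = 93.4%.

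**Joint power of the listed pair.** MOT appears in both contrasts with opposite sign. The correlation of the two estimates is −(116²/70)/(19.61 × 24.01) = −0.41. The bivariate normal probability that both reject is 73.0%.

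**Simulation** (1,000,000 trials, normal data, pooled t with 172 df or F; chi-square likelihood ratio test in the last column):

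| Criterion at 35/70/70, 2.5% each | t/F | LRT |
|---|---|---|
| Three-group test and EXE vs MOT (sample-size pair) | 78.8% | 79.4% |
| EXE vs MOT alone | 78.8% | 79.4% |
| MOT vs CON alone | 93.1% | 93.4% |
| EXE vs MOT and MOT vs CON (listed pair) | 72.2% | 73.1% |
| At least one of the listed pair | 99.7% | 99.7% |

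The first row reproduces the plan's 80% to within about one point. The three-group test alone rejects in 99.99% of trials, so that row is simply the power of EXE vs MOT. If the sample-size wording is instead read as requiring all three pairs to differ, the joint power is again 72.2% (73.1%). Of these two readings, only the overall three-group one reproduces the stated figure.

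**Women needed for 80% on both listed tests under Bonferroni (t).** 39/78/78 gives 78.9%; 40/80/80 gives 80.4%. That is 200 evaluable, or 200/0.8 = 250 randomised instead of 220.

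**Baseline adjustment.** The SAP gives no correlation r between baseline and outcome, so r is an assumption. Multiplying the SD by √(1 − r²), joint power (t) is 74.8% at r = 0.2, 78.1% at 0.3 and 82.5% at 0.4. It reaches 80% at about r = 0.32 (LRT) to 0.35 (t).

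**Holm instead of Bonferroni, same women.** EXE vs MOT 85.9% (LRT 86.4%), MOT vs CON 96.0% (96.2%), both 82.2% (82.8%). Family-wise error with t tests: 4.7% under the global null, 4.7% with only EXE vs MOT null, 4.3% with only MOT vs CON null. With the asymptotic chi-square reference, one configuration gave about 5.2–5.3%.

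**The case against.** The strongest reply is that Section 2 does name a pair. It is the only numbered list of hypotheses, and Section 4 can be read as pointing back to it, with the sample-size text describing just a planning scenario. That is a fair reading, and EXE vs MOT is common to both pairs in any case. But it does not rescue the power statement: if Section 2 governs, the 80% was calculated for a different pair.

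Other points on the power:

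- *Baseline adjustment may recover it.* This stands. An r of about 0.32–0.35 is enough, so a shortfall in the adjusted analysis is not established. Adequacy is not established either, since no r is stated.
- *Intention to treat includes everyone randomised.* At 44/88/88 the joint power would be about 85–86%, but that is an upper bound which sets aside the plan's own 20% loss.
- *The listed hypotheses are directional.* One-sided 2.5% per test would give 82.8%, but the SAP nowhere states one-sided testing, and likelihood ratio tests of equality are not directional.
- *Each listed test is reasonably powered alone.* True, at about 79% and 93%. The joint criterion is the one the sample-size section itself adopts.

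Bonferroni is valid, and leaving EXE vs CON without a confirmatory test is a legitimate choice once it is stated. The sample-size figure is not available in the text at hand, so the three-group reading rests on its reproducing the stated 80%.

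**Conclusion.** The concern holds. The objectives and the sample size give different second primary tests, and Section 4 does not settle which one takes the 2.5%. The stated 80% is right, to about one point, for the three-group test plus EXE vs MOT. For the two listed hypotheses together it is about 72–73%. The chance of missing at least one of them is then about 27–28%, against the nominal 20% (about 21% as reproduced).

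These figures rest on the plan's means and SD, 35/70/70 evaluable, two-sided 2.5% per test and no gain from baseline adjustment. The mismatch between sections depends on none of these. It should be fixed; it does not make the trial unsound, and it does not show that the adjusted analysis will be underpowered.

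**What to change.** 1. **Name the same two primary hypotheses** in Section 2, Section 3 (Sample size) and Section 4.
   - If they are EXE vs MOT and MOT vs CON, restate the power: *With 35/70/70 evaluable women, SD 116 and two-sided 2.5% per test, power is about 79% for EXE vs MOT, 93% for MOT vs CON and 72–73% for both, before baseline adjustment.*
   - If they are the three-group test and EXE vs MOT, keep about 79% and state that MOT vs CON is not a confirmatory test.
2. **If the listed pair is kept, replace Bonferroni with Holm:** test the smaller p-value at 2.5% and, only if it rejects, the larger at 5%. Holm rejects everything Bonferroni rejects, holds the family-wise error at 5% and gives about 82% for both. Use t/F reference distributions, because the chi-square approximation slightly exceeded 5% in one configuration.
3. **State the status of EXE vs CON in one sentence:** estimated with a 95% confidence interval, no confirmatory test. Bringing it in through a closed procedure (three-group test at 5%, then pairwise tests at 5%) is optional.

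The cost is a dated SAP amendment, made before outcome data are analysed by group because the trial is already running. No more women are needed. With the listed pair under Bonferroni, the published power figure becomes less favourable. With Holm, the second-step level rises from 2.5% to 5%, but only after the first test has rejected.
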